## Statistical Analysis Plan

Sponsor Name: Nitto Denko Corporation  
Sponsor Protocol ID: ND-L02-s0201-005

### 1. Source Documents

The Statistical Analysis Plan (SAP) was written based on the following documentation:

Document	Date	Version
Protocol Amendment	17 June 2020	5.0
eCRF	19 February 2021	Prod 3.00

### 2. Protocol Details

#### 2.1 Study Objectives

Primary:

- Evaluate the safety and tolerability of ND-L02-s0201, administered at 2 dose levels, once every 2 weeks (Q2W) over 24 weeks, versus placebo, in conjunction with standard of care

Secondary:

- Evaluate the biological activity of ND-L02-s0201 as measured by spirometry over 24 weeks
- Evaluate changes of interstitial lung abnormalities (ILA) as measured by high-resolution computed tomography (HRCT)

- [REDACTED]
- [REDACTED]

#### 2.2 Overall Study Design

This is a Phase 2, double-blind, placebo-controlled, randomized, multicenter, international study of 2 doses of ND-L02-s0201 for Injection, consisting of 3 treatment arms: 2 dose levels of ND-L02-s0201, a low dose (45 mg) and a high dose (90 mg), will be evaluated in 2 arms; a third arm will be administered placebo. This study will evaluate safety, tolerability, biological activity, and PK in subjects with a diagnosis of idiopathic pulmonary fibrosis (IPF) with forced vital capacity (FVC)  $\geq 45\%$  of predicted and diffusion capacity of the lung for carbon monoxide (DLCO)  $\geq 30\%$  of predicted.

Approximately 120 eligible subjects will be randomized 1:1:1 to 1 of following 3 treatment arms:

- ND-L02-s0201 for Injection high dose (90 mg)

## Statistical Analysis Plan

Sponsor Name: Nitto Denko Corporation  
Sponsor Protocol ID: ND-L02-s0201-005

- ND-L02-s0201 for Injection low dose (45 mg)
- Placebo.

The randomization via the interactive web response system (IWRS) will be stratified by the receipt of standard of care at the enrollment of the study, defined as administration of either nintedanib or pirfenidone, or no standard of care. As there is no minimum number of subjects for a given strata of standard of care, balance in strata across the 3 treatment arms is required.

Eligible subjects who meet the inclusion criteria and do not meet any of the exclusion criteria and have provided informed consent will be enrolled in the study. Subjects will participate in the study for approximately 40 weeks consisting of a Screening and Baseline period of up to 6 weeks, a treatment period of 24 weeks including a total of 12 doses and an End-of-Treatment visit 2 weeks after the final dose (Visit 14), and a follow-up visit 4 and 10 weeks after Visit 14, or until they withdraw from the study or the study is terminated by the Sponsor. During the treatment period ND-L02-s0201 for Injection will be administered by intravenous (IV) infusion Q2W ( $\pm$  4 days for Visit 3 or  $\pm$  7 days for Visits 4 to 13, ensuring a minimum of 7 days between each dose) for a total of 12 doses. Subjects may be premedicated to mitigate the risk of infusion-related reactions at the discretion of the Investigator.

### 2.3 Sample Size and Power

Approximately 120 subjects will be enrolled into the study, with approximately 40 subjects in each of 3 arms. The study will include approximately 35-40 sites, and will enroll approximately 3 to 5 subjects per site.

## 3. Efficacy and Safety Variables

### 3.1 Primary Endpoints

#### Safety

- Incidence of TEAEs and treatment-emergent SAEs
- Proportion of subjects discontinuing study treatment due to TEAEs

### 3.2 Secondary Endpoints

#### Biological Activity

## Statistical Analysis Plan

Sponsor Name: Nitto Denko Corporation  
Sponsor Protocol ID: ND-L02-s0201-005

- Rate of decline in FVC from baseline to Visit 14 (Day 169) (measured in L and % of predicted over unit time)
- Absolute and relative change in FVC (L and % of predicted) at Visit 14 (Day 169) as compared with baseline
- Proportion of subjects with an FVC response (L and % of predicted) defined as either having improvement or a decline by 0% to  $\leq 5\%$ ,  $> 5\%$  to  $\leq 10\%$ , and by  $> 10\%$  at Visit 14 (Day 169)
- Change in DLCO (mL/min/mmHg) and DLCO (mL/min/mmHg) corrected for hemoglobin at Visit 14 (Day 169)
- Changes of ILA as measured by HRCT (i.e., change in parenchymal feature [Baseline to Visit 14 (Day 169)]), as determined by qualitative assessment (central radiologist) and quantitative analysis (Quantitative Lung Fibrosis – QLF analysis)
- Time to first acute IPF exacerbation (i.e., an unexplained worsening of dyspnea, evidence of hypoxemia as defined by worsened or severely impaired gas exchange, new radiographic alveolar infiltrates, and an absence of an alternative explanation such as infection, pulmonary embolism, pneumothorax, or heart failure [Raghu et al, 2011]) or death
- Rate of hospitalization for respiratory ailments and time to first hospitalization for respiratory ailments or death
- Rate of mortality due to all causes and overall survival
- Rate of deterioration of IPF resulting in lung transplantation (up to 12 weeks after the end of study treatment) or death and time to deterioration of IPF resulting in lung transplantation (up to 12 weeks after the end of study treatment) or death

[REDACTED]

- [REDACTED]
- [REDACTED]
- [REDACTED]

### 3.4 Efficacy and Safety Variables

#### 3.4.1 Spirometry

Spirometry variables include forced vital capacity (FVC) and percent predicted FVC (%FVC). FVC will be measured in units of liters (L) and rounded to 2 decimal places. %FVC will be measured in percent and rounded to 2 decimal places. The spirometry

## Statistical Analysis Plan

Sponsor Name: Nitto Denko Corporation  
Sponsor Protocol ID: ND-L02-s0201-005

variables will be provided by an external vendor in a data transfer and the results will not be entered into the EDC system.

In the event that no baseline measurement is designated, then the baseline measurement will be the last non-missing value before the first infusion of study treatment.

### 3.4.2 Diffusion Capacity of the Lung for Carbon Monoxide (DLco)

Diffusion capacity of the lung for carbon monoxide (DLco) in mL\*(CO/min/mmHg) will be provided by an external vendor in a data transfer, and the results will not be entered in the EDC system. DLco will be provided with and without correction for hemoglobin and results will be rounded 2 decimal places.

In the event that no baseline measurement is designated, then the baseline measurement will be the last non-missing value before the first infusion of study treatment. Values not designated as "Accepted" in the vendor data transfer will be excluded from statistical analyses. When more than two valid test values are obtained at a study visit in the event a PFT that has passed QC shows declines from baseline that need confirmatory testing, the average of both values will be included in the summary table.

### 3.4.3 High Resolution Computed Tomography (HRCT)

High resolution computed tomography (HRCT) data will be provided by a central reader and will include variables from qualitative and quantitative analyses of HRCT scans

Results of HRCT analyses will be provided by an external vendor in a data transfer and will not be entered in the EDC system

#### 3.4.3.1 Qualitative HRCT Variables

The qualitative HRCT variables will include central reader estimates of the extent of lung region abnormalities by lung (left and right) and region (upper, mid, and lower).

**Statistical Analysis Plan**

Sponsor Name: Nitto Denko Corporation  
Sponsor Protocol ID: ND-L02-s0201-005

[REDACTED]

Possible values (as %) for each region will include "Absent", "1-25", "26-50", "51-75", and "76-100". Results for unreadable scans will be reported as "Unknown".

The central reader's assessment of overall change in interstitial lung disease (ILD) from baseline to Visit 14 (or ET) will have possible values of "Much Better", "Better", "Same", "Worse", "Much Worse", or "Unknown".

[REDACTED]

[REDACTED]

	[REDACTED]					
[REDACTED]						
[REDACTED]						
[REDACTED]						
[REDACTED]						
[REDACTED]						

**3.4.3.2 Quantitative HRCT Variables**

[REDACTED]

- [REDACTED]
- [REDACTED]
- [REDACTED]
- [REDACTED]
- [REDACTED]
- [REDACTED]

[REDACTED]

## Statistical Analysis Plan

Sponsor Name: Nitto Denko Corporation  
Sponsor Protocol ID: ND-L02-s0201-005

- Treatment compliance =  $100 * \text{total actual cumulative dose of administered (mg)} / \text{total cumulative dose of the planned (mg)}$  during the study.

Where the cumulative dose of planned dose is defined as number of planned doses until last dose subject received multiplying by assigned dose (45 mg for low dose treatment arm and 90 mg for high dose treatment arm). The total planned dose is defined as the number of infusions planned until subject's last dose (i.e. if subject's last dose is at Week 22, then the subject's expected number of infusions would be 12).

If date of first dose date is missing, then the randomization visit will be used. The last dose is the date of the last dose administered as of the data cut-off date.

### 3.4.6 Adverse Events (AEs)

All AEs recorded on the eCRF will be coded using the latest version of MedDRA dictionary, per the Data Management Plan, throughout the study and classified as either pre-treatment AEs or TEAEs as follows:

- Pre-treatment AEs are events that started prior to the first dose of any study treatment, including pre-medication.
- TEAEs are events that occur on or after the first dose of any study treatment including pre-medication through two weeks after the last dose of study treatment or adverse events which start before the first dose of study treatment, but increase in severity after the first dose through two weeks after the last dose of study treatment.

Assessment of AE severity will be based on the National Cancer Institute (NCI) Common Terminology Criteria for Adverse Events version 5.0 (CTCAE v5.0). The severity of all AEs is recorded as mild (Grade 1), moderate (Grade 2), severe (Grade 3), life threatening consequences (Grade 4), or death (Grade 5), per CTCAE grading. If severity is missing for a TEAE, it will be considered severe only in the overall category in the summary tables.

The relationship between an AE and study treatment is assessed as definite, probable, possible, unlikely, or none. A drug-related AE is an AE considered by the investigator as definitely, probably, possibly, or unlikely related to study treatment. If the relationship is unknown or missing, it is also considered as related to study treatment.

AEs of special interest (AEOI) include [REDACTED] respiratory adverse events, and acute exacerbation of idiopathic pulmonary fibrosis.

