### **13.2.3. Safety**

All safety analyses will be performed on the safety population.

The analysis of safety, reported for each treatment arm, will be based on the frequency of AEs and their severity for all treated subjects. The safety variables, including AEs, SAEs, and AEs of interest (coded using the Medical Dictionary for Regulatory Activities [MedDRA]), clinical laboratory tests [REDACTED] physical examination, ECGs, and vital signs will be summarized or tabulated by treatment arm. Some of the variables will be tabulated by treatment arm and by visit. Incidence of AEs will be further tabulated by subjects on SOC within each treatment arm.

The proportion of subjects discontinuing study treatment due to AEs will be tabulated by treatment arm.

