### **14.2. Adverse Event Classification**

#### **14.2.1. Treatment-Emergent Adverse Events**

An AE is defined as treatment-emergent if it occurs at or after the first dose of study treatment and through 2 weeks after the last dose of study treatment. This also includes AEs which are observed before the first dose of study treatment and increase in severity after the first dose through 2 weeks after the last dose of study treatment.

Note: 2 weeks after the last dose of study treatment was selected because it is expected to be longer than 5 times the terminal half-life of ND-L02-s0201.

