### **14.5. Documentation of Adverse Events by Investigator**

Subjects will be evaluated and questioned generally to identify AEs during the course of the study. Adverse event collection will begin 24 hours before Visit 1a. Adverse events that occur up to and including 12 weeks after administration of the last dose of study treatment, including ET, must be reported.

All AEs spontaneously reported by the subject and/or in response to an open question from study personnel or revealed by observation, physical examination, or other diagnostic procedures will be recorded on the Adverse Event Form for that visit. Any clinically relevant deterioration in laboratory assessments, intercurrent illness, or other clinical findings is considered an AE and must be recorded on the Adverse Event Form. In addition, an abnormal test finding will be classified as an AE if one or more of the following criteria are met:

- The test finding is accompanied by clinical symptoms.
- The test finding necessitates additional diagnostic evaluation(s) or medical/surgical intervention; including significant additional concomitant drug treatment or other therapy. Note: simply repeating a test finding, in the absence of any of the other listed criteria, does not constitute an AE.
- The test finding leads to a change in study treatment dosing or discontinuation of subject participation in the clinical research study.
- The test finding is considered an AE by the Investigator.

Wherever possible, a specific disease or syndrome rather than individual associated signs and symptoms should be identified. However, if an observed or reported sign or symptom is not considered a component of a specific disease or syndrome by the Investigator, it should be recorded as a separate AE. Laboratory data will be collected as stipulated in this protocol. Clinical syndromes associated with laboratory abnormalities will be recorded as appropriate (eg, diabetes mellitus rather than hyperglycemia).

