## **14.6. Notification about Serious Adverse Events and Serious and Unexpected Suspected Adverse Reactions**

### **14.6.1. Investigator Reporting to Sponsor**

All SAEs that occur during the course of the study must be reported by the Investigator to the Sponsor, designated representative, and Medical Monitor within 24 hours by fax or email. In addition, all SAEs that occur up to and including 12 weeks after administration of the last dose of study treatment must be reported to the Sponsor within 24 hours from when the Investigator becomes aware of the SAE.

Investigators must report to the Sponsor all SAEs, whether or not considered drug-related, including those listed in the Investigator Brochure. The report must include an assessment of causality.

For all SAEs, the Investigator is obligated to obtain and provide information to the Sponsor in accordance with the timeframes for reporting specified above. In addition, an Investigator may be requested by the Sponsor to obtain specific additional follow-up information in an expedited fashion. This information may be more detailed than that captured on the AE CRF. In general, this will include a description of the AE in sufficient detail to allow for a complete medical assessment of the case and independent determination of possible causality. Information on other possible causes of the event, such as concomitant medications and illnesses must be provided. In the case of a subject death, a summary of available autopsy findings must be submitted as soon as possible to the Sponsor or its designated representative.

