## Statistical Analysis Plan

Sponsor Name: Nitto Denko Corporation  
Sponsor Protocol ID: ND-L02-s0201-005

This summary table will be repeated for each of the following COVID-19 vaccination status:

- Subjects vaccinated prior to start of study treatment
- Subjects vaccinated while on treatment
- Subjects not vaccinated

The number and percentage of subjects reporting each TEAE will be summarized by System Organ Class (SOC) and Preferred Term (PT) by treatment arm and overall for the SAF population. Tables will be sorted alphabetically by SOC. PTs will be sorted by descending overall total. The following summaries will be produced:

- TEAEs, by SOC and PT;
- TEAEs by PT; this table will also be repeated for each COVID-19 vaccination status as described above;
- TEAEs with frequency >10% in one or more treatment arms by PT;
- TEAEs related to the study treatment, by SOC and PT;
- TEAEs related to the study treatment, by PT;
- TEAEs by relationship to the study treatment, by SOC and PT;
- TEAEs related to pre-medication, by SOC and PT;
- TEAEs by maximum severity and PT;
- TEAEs related to the study treatment by maximum severity and PT;
- TEAEs leading to the study treatment interruption, by SOC and PT;
- TEAEs leading to the study treatment withdrawn, by SOC and PT;
- TEAEs related to the study treatment leading to the study treatment withdrawn, by SOC and PT;
- Serious TEAEs, by SOC and PT;
- Serious TEAEs related to the study treatment, by SOC and PT;
- Serious TEAEs with frequency >5% in one or more treatment arm by PT;

In the above summaries, subjects with more than one AE within a particular SOC are counted only once for that SOC. Similarly, subjects with more than one AE within a particular PT are counted only once for that PT. For summaries by maximum severity, subjects with multiple AEs within a particular SOC or PT will be counted under the category of their most severe AE within that SOC or PT. AEs with missing severity will be included as severe in the overall count of subjects with AEs, but will not be included in the counts of subjects with AEs within a SOC or PT.

The number and percentage of subjects with at least 1 treatment-emergent AEOI, and each type of treatment-emergent AEOI will be summarized. The number and percentage of subjects reporting at least 1 treatment-emergent AEOI will be summarized by SOC and PT for the following in the SAF population:

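### AEs and SAEs starting more than 2 and up to 12 weeks after the last dose have no class in SAP 3.4.6 and enter no readable by-arm AE table in SAP 7.6.2

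*SAP*

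**What the plan says.** **Collection.** Protocol 14.5 states: "Adverse events that occur up to and including 12 weeks after administration of the last dose of study treatment, including ET, must be reported". Protocol 14.6.1 sets the same limit for serious events: "all SAEs that occur up to and including 12 weeks after administration of the last dose of study treatment must be reported". Both follow-up visits, Visit 15 and Visit 16, record AEs (Protocol 12.4).

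**Classification.** SAP 3.4.6 has all AEs on the eCRF "classified as either pre-treatment AEs or TEAEs as follows". The first class is closed at the first dose: "Pre-treatment AEs are events that started prior to the first dose of any study treatment, including pre-medication". The second runs from the first dose, pre-medication included, to two weeks after the last dose, and also takes in earlier events that worsen within that window. No third class is given. Protocol 14.2.1 gives the reason for the window: "2 weeks after the last dose of study treatment was selected because it is expected to be longer than 5 times the terminal half-life".

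**Reporting.** Protocol 13.2.3 describes a safety analysis "based on the frequency of AEs and their severity for all treated subjects" and has AEs, SAEs and AEs of interest summarised or tabulated by arm. In SAP 7.6.2 the overview table, the system organ class and preferred term tables, the severity, relatedness and serious-event tables, and the AE-of-interest tables are all restricted to treatment-emergent events. The rows for drug-related SAEs and AEs of interest in the overview fall under its TEAE heading. All AE data are listed with a treatment-emergence flag, and there are separate listings of SAEs and of AEs resulting in death.

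**The concern.** A classification offered as covering all AEs should place each one. This one does not: a new event in, say, the fifth week after the last dose must be reported, but it is neither pre-treatment nor treatment-emergent. The gap then carries into the outputs, because the AE tables are built on the treatment-emergent class.

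Safety against placebo is the primary objective. A reader of the tables would see no arm-by-arm count of, for example, cardiac, hepatic or renal SAEs starting in the follow-up period, though the trial schedules visits to collect them. The readable part of SAP Section 8, which lists departures from the protocol analyses, does not mention the narrowing from AEs to TEAEs.

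**Working it through.** **Inputs.** Twelve doses every two weeks from Day 1 (Protocol 7.1, Table 1). TEAE window ends 14 days after the last dose (SAP 3.4.6, Protocol 14.2.1). AE and SAE reporting ends 84 days after it (Protocol 14.5, 14.6.1). About 40 subjects per arm (SAP 2.3).

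**Reproducing the protocol's calendar.** Dose k falls on Day 1 + 14(k − 1).
- Dose 12: 1 + 14 × 11 = Day 155.
- End of TEAE window: 155 + 14 = Day 169, the nominal Visit 14.
- End of AE reporting: 155 + 84 = Day 239, the nominal Visit 16.
- With 42 days of screening: 42 + 239 = 281 days, the maximum participation in Protocol 7.1.

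**Length of the unclassified interval.** 84 − 14 = 70 days. The last-dose day cancels, so this is the same for every subject whenever treatment stopped.

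**Share of post-baseline collection.** Share = 70 / (last-dose day + 84).

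| Doses received | Last-dose day | End of reporting | Unclassified days | Share |
|---|---|---|---|---|
| 12 | 155 | 239 | 70 | 29% |
| 6 | 71 | 155 | 70 | 45% |
| 3 | 29 | 113 | 70 | 62% |
| 1 | 1 | 85 | 70 | 82% |

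Only the denominator changes down the table.

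**Person-time per arm**, assuming 40 subjects who all receive 12 doses: 40 × 70 / 365.25 = 7.7 person-years unclassified, out of 40 × 239 / 365.25 = 26.2.

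**Rough number of events.** The documents give no SAE rate. If the rate were constant and between 0.1 and 0.6 per person-year (an assumed range), the interval would hold about 0.1 × 7.67 = 0.8 to 0.6 × 7.67 = 4.6 SAEs per arm. The 169 days to the end of the TEAE window would hold about 1.9 to 11.1. These counts include SAEs that have their own analysis elsewhere, so they overstate what is lost from every by-arm table.

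**What is analysed by arm after the window.**

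| Late information | By-arm analysis in readable text |
|---|---|
| Death from any cause; transplantation or death | Yes, rates and time to event (SAP 7.5.2.5) |
| First acute IPF exacerbation or death | Yes (SAP 7.5.2.4) |
| Respiratory hospitalisation | Yes (SAP 7.5.2.5) |
| Laboratory values, vital signs, SpO2 | Yes, by-visit summaries (SAP 7.6.3, 7.6.4) |
| Other SAEs, other AEs, and fatal AEs by preferred term | No, listings only (SAP 7.6.2) |

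**The case against.** The best defence is that the two-week window is deliberate. The protocol defines it, gives a half-life reason, and words the primary endpoints as TEAEs and treatment-emergent SAEs, so the primary analysis is complete as planned. Protocol 13.2.3 is a general statement, and Section 13 leaves the detail to the SAP. Late events are not lost: they are listed, SAP 7.1 has listings presented by treatment arm, and with about 40 subjects per arm a reader could count SAEs by hand. The gravest IPF outcomes have their own analyses.

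Most of that stands, and it limits the point to what is left over. It does not supply a class for events the protocol requires to be reported. A half-life argument explains where treatment-emergent ends, not why later events go uncounted, and a listing gives no numerators and percentages by arm.

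Three stronger readings are tempting, and the documents do not support them.
- *Subjects who stop early are affected most, so the arm comparison is biased.* A reader might infer this from the rise from 29% to 82%. The interval is 70 days for everyone, and early stopping shortens the tabulated time without lengthening the untabulated time. No discontinuation or late-event rates are given from which a bias could be shown. On the nominal two-week schedule, an AE that causes the next dose to be withheld would normally start inside the window anyway.
- *Nothing in follow-up is tabulated.* Laboratory values, vital signs and the IPF outcomes above are.
- *The 90-day contraception and breastfeeding restrictions show that the TEAE window is too short.* The documents do not link those restrictions to the attribution of AEs.

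Two bullets at the end of SAP 7.6.2, part of Section 8 and some other safety text are redacted. The absence of a table is therefore established only for the readable text. The two-class sentence in 3.4.6 is fully readable.

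**Conclusion.** The point holds in limited form. AEs and SAEs starting more than 2 and up to 12 weeks after the last dose belong to no class in SAP 3.4.6 and, as far as the text can be read, to no by-arm AE or SAE table in 7.6.2. The interval is 70 days per subject, 29% of planned post-baseline AE collection for a 12-dose completer, and about 7.7 of 26.2 person-years per arm if 40 subjects per arm all complete. The practical loss is by-arm counts of late events other than death, IPF exacerbation, respiratory hospitalisation and transplantation. The primary endpoint and the TEAE window are not in question, and no difference between arms is shown. It is a gap in completeness for a trial whose primary objective is safety, and worth closing because it is cheap to close.

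**What to change.** Leave the TEAE definition and the primary endpoint as they are.

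1. In SAP 3.4.6 add a third class, *post-treatment AE*: onset more than 2 weeks and up to 12 weeks after the last dose of study treatment.
2. In SAP 7.6.2 add a by-arm summary of post-treatment AEs, and of post-treatment SAEs, by system organ class and preferred term in the safety population.
3. In the same section add one by-arm table of SAEs and fatal AEs from the first dose to 12 weeks after the last dose.
4. If a redacted bullet already provides one of these tables, only the class in 3.4.6 and the remaining tables are needed.

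The cost is a short change of SAP wording and a few extra tables. The data are already collected, and no visit, procedure or endpoint changes. Making the change before unblinding avoids any suggestion that the tables were chosen on the results.
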